| Description of Study Intervention: | We will use the NEUROCONN DC Stimulator Plus for investigational purposes to deliver either cross-frequency delta-beta, cross-frequency theta-gamma, or active sham transcranial alternating current stimulation. Active sham treatment will include 20 seconds of ramp in to 40 seconds of tACS with a ramp out of 20 seconds for a total of 80 seconds of stimulation. The choice of an active sham is motivated to enhance success |

of participant blinding by mimicking skin sensations associated with tACS. Theta-gamma and delta-beta tACS will also have a 20 second ramp in and ramp out for each task block. With 8 total task blocks each lasting 5 minutes, participants receive a total of 40 minutes of stimulation. Stimulation waveform is a low-frequency sine wave with a superimposed high-frequency sine-wave at the peak of each cycle. The zero-to-peak amplitude of stimulation is 2mA.

Study Duration:

2 years

Participant Duration:

Participation for each participant will be 2 weeks. Completion includes three sessions: a clinical assessments session, a stimulation session, and an MRI session. The clinical assessments session will take approximately 2 hours. The stimulation session will take approximately 3 hours. The visit to the MRI takes approximately 1.5 hour. We estimate that total participation to be approximately 6.5 hours.

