1.3 SCHEDULE OF ACTIVITIES (SOA)

| | Phone Screening | Online Assessments | Session 1 Clinical Assessments | Session 2 - Stimulation | Session 3 - MRI |
|--------------------------------|-----------------|--------------------|--------------------------------|-------------------------|-----------------|
| Procedures | | | | | |
| Informed consent | X (verbal) | X (digital) | X (written) | | |
| Determine Eligibility | X | X | X | | |
| PHQ-8 (without suicide q.) | | X | | | |
| PHQ-9 | | | X | | |
| SHAPS | | X | X | X | |
| Demographics | | | X | | |
| Medical history | | | X | | |
| MINI (diagnostic) | | | X | | |
| C-SSRS | | | X | | |
| Maudsley Staging Method | | | X | | |
| HAM-D | | | X | | |
| RRS | | | X | | |
| BIS/BAS | | | X | | |
| SHAPS | | | X | | |
| C-SSRS | | | X | | |
| TEPS | | | X | | |
| Beck Depression Inventory - II | | | X | | |
| BAS/BIS | | | X | | |
| STAI | | | X | | |
| Urine Pregnancy Test | | | | X | |
| Randomization | | | | X | |
| Resting-state EEG | | | | X | |
| EEfRT | | | | X | |
| EEfRT with tACS | | | | X | |
| Intermittent resting-state EEG | | | | X | |
| Stimulation Questionnaire | | | | X | |
| AE Structured Interview | | | | X | |
| AE Review and Evaluation | | | | * | |
| Structural MRI | | | | | X |
| Resting-state MRI | | | | | X |
| Functional MRI with EEfRT | | | | | X |

* when applicable

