| To investigate whether functional connectivity between dorsal striatum and left lateral prefrontal cortex predicts individual differences in the impact of delta-beta tACS on performance. | Functional connectivity analysis of resting-state functional magnetic resonance imaging is correlated with the impact of tACS on behavior. | Previous research has suggested that frontal-striatal connectivity is related to reward-based decision-making. Participants with anhedonia may show reduced connectivity within this neural circuit that is predictive of the impact of tACS on reward-based decision-making. |

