For the third session, participants are instructed to arrive at the Biomedical Research Imaging Center (BRIC) in Marsico Hall on UNC-CH campus. Participants are instructed to arrive at the facility 30 minutes early to ensure that they are ready to go into the MRI for the 60-minute allotted timeslot. During the 60 minutes of scanning, a 5-minute structural MR is acquired, 10-minutes of functional MR scans during the eyes-open resting-state are acquired, and the remaining time is used to complete as many blocks of the EEfRT as possible. Completion of the MRI session is not required for the dataset to be considered a complete dataset. These additional data acquisitions enable exploratory analyses that will be used to design future studies.

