Retention is primarily achieved by condensing the bulk of the experiment into a single stimulation session. The payment is \$30 for completion of virtual clinical assessments session. Then, completion of the stimulation during task provides an addition \$50. Finally, participants are invited back for a third session that is an MRI session which provides \$40. Thus, completion of all study requirements gives \$120. However, completion of the in-person stimulation session is sufficient to address all primary and secondary outcomes. The participant will receive payment at the end of each session on a payment card that can be loaded. The research staff will also give each participant a reminder call or email for upcoming sessions. Each research staff member will be available for the participants to contact via email or phone.

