7. STUDY INTERVENTION DISCONTINUATION AND PARTICIPANT DISCONTINUATION/WITHDRAWAL

7.1 DISCONTINUATION OF STUDY INTERVENTION

Discontinuation of stimulation during session 1 means that study participation is halted and no other sessions are completed. If a clinically significant finding is identified after enrollment, the investigator or qualified designee will determine if any change in participant management is needed. Any new clinically relevant finding will be reported as an adverse event (AE).

The study intervention (i.e., 40 minutes of stimulation spaced by intermittent resting-states) will be discontinued for the following reasons:

- Any clinical adverse event (AE), laboratory abnormality, intercurrent illness or other medical condition, or situation occurs such that continued participation in the study would not be in the best interest of the participant.
- The participant meets any exclusion criteria (either newly developed or not previously recognized).

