9.1 STATISTICAL HYPOTHESES

- Primary Outcome hypothesis:
 - Null: There is no difference in goal-directed behavior between baseline EEFRT and EEFRT during stimulation as a function of stimulation type (delta-beta tACS, theta-gamma tACS, or active-sham).
 - Alternate: There is a difference in goal-directed behavior between baseline EEFRT and EEFRT during stimulation as a function of stimulation type (delta-beta tACS, theta-gamma tACS, or active-sham).
- Secondary Outcome hypothesis:
 - Null: There is no difference in delta-beta phase-amplitude coupling strength between prefrontal electrodes and left motor electrodes for post-stimulation resting-state periods as a function of stimulation type (delta-beta tACS, theta-gamma tACS, or active-sham).

- Alternate: There is a difference in delta-beta phase-amplitude coupling strength between prefrontal electrodes and left motor electrodes for post-stimulation resting-state periods as a function of stimulation type (delta-beta tACS, theta-gamma tACS, or active-sham).
- Exploratory Outcome hypothesis 1:
 - Null: The impact of delta-beta tACS on goal-directed behavior is not correlated with motivation symptom severity.
 - Alternative: The impact of delta-beta tACS on goal-directed behavior is correlated with motivation symptom severity.
- Exploratory Outcome hypothesis 2:
 - Null: Functional connectivity during the resting-state between dorsal striatum and lateral prefrontal cortex is not predictive of the impact of delta-beta tACS on goal-directed behavior.
 - Alternative: Functional connectivity during the resting-state between dorsal striatum and lateral prefrontal cortex is predictive of the impact of delta-beta tACS on goal-directed behavior.

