9.4.4 ANALYSIS OF THE EXPLORATORY OUTCOMES

First exploratory outcome: symptom dimensions

A two-dimension factor analysis will be run on all sub-scores from clinical assessments to derive a mood and motivation composite symptom score. This analysis was used in our previous study and found that goal-directed behavior negatively correlated with motivation symptoms. Thus, we hypothesize that the severity of motivation symptoms will correlate with the degree to which delta-beta tACS will increase goal-directed behavior. The analysis will be run as a Pearson correlation within the group that received delta-beta tACS. To control for the specificity of this effect, this correlation will be compared to sham tACS, mood symptoms, and reward-evaluation.

Second exploratory outcome: functional connectivity in frontal-striatal circuitry

Using the resting-state functional magnetic resonance imaging data, we will calculate the strength of functional connectivity between the dorsal striatum and the lateral prefrontal cortex. We hypothesize that participants with major depressive disorder and anhedonia will show decreased strength in connectivity, and that individual differences in this functional connectivity strength will be predictive of the change in goal-directed behavior with delta-beta tACS. The analysis will be run as a Pearson correlation within the group that received delta-beta tACS. To control for the specificity of this effect, this correlation will be compared to sham tACS and reward-evaluation.

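### Exploratory outcome 2 claims that fronto-striatal connectivity predicts the delta-beta tACS effect, but the only scan follows stimulation and the behavioural outcome, so it can show association only

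*Combined protocol and SAP*

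**What the plan says.** Three places give connectivity the role of a predictor. The objective in section 3 asks whether dorsal striatum to left lateral prefrontal connectivity "predicts individual differences in the impact of delta-beta tACS on performance". The alternative hypothesis in section 9.1 reads: "Functional connectivity during the resting-state between dorsal striatum and lateral prefrontal cortex is predictive of the impact of delta-beta tACS on goal-directed behavior". Section 9.4.4 expects that "individual differences in this functional connectivity strength will be predictive of the change in goal-directed behavior with delta-beta tACS". The outcome column of section 3 is more modest and says only that connectivity is correlated with the behavioural effect.

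The order of sessions is consistent. The synopsis (1.1) states: "Completion includes three sessions: a clinical assessments session, a stimulation session, and an MRI session". In the schedule of activities (1.3), resting-state MRI is marked once, in the last column: "Resting-state MRI | | | | | X". Section 4.1 puts randomisation, four baseline EEfRT blocks and eight stimulated blocks (about 40 minutes of tACS) in the second session and the scan in the third. Section 5.5 confirms that "participants are invited back for a third session that is an MRI session".

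The analysis (9.4.4) is a Pearson correlation within the delta-beta arm, compared with the sham arm and with reward-evaluation. No interval between stimulation and scan is given. The only bound is the two-week total participation in the synopsis.

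**The concern.** To support a claim of prediction, a variable should be measured before the treatment whose effect it is meant to predict. Here it is measured after both the treatment and the outcome. If delta-beta tACS altered this circuit more in people who responded more, Session 3 connectivity would correlate with the behavioural change even if connectivity before stimulation predicted nothing.

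The trial has reason to consider this. Section 2.2 names the dorsolateral prefrontal to dorsal striatum circuit as a subject of the experiment, and the secondary objective looks for a change in neural coupling that outlasts the stimulation. Carry-over on connectivity is nevertheless not discussed. What is at stake is the meaning of a positive result. Section 4.1 says the MRI data will inform later studies, and a study planned around a baseline predictor would need evidence that connectivity comes before the response.

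**Working it through.** The plan gives no power, effect size or sample-size figure for exploratory outcome 2, so there is no stated figure to reproduce. The check has three parts.

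**1. Order of measurement.** Baseline behaviour, stimulation and during-stimulation behaviour all fall in Session 2; connectivity falls in Session 3. Some sections (7.1, 9.3, 9.4.1) number the sessions differently and call the stimulation session the first, but under either numbering the scan comes after stimulation. No pre-stimulation scan is listed anywhere.

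**2. Can the sham contrast separate the explanations?** Arm size is 8 per cell × 2 anhedonia levels = 16 (section 4.1), and this is a maximum because the MRI is optional. Alpha is 0.05 (9.4.1). Let C be pre-stimulation connectivity and E an independent individual response, both with SD 1. The slope b is an assumption.

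- True prediction, no carry-over: measured connectivity = C; behavioural change = E + bC.
- Pure carry-over, no prediction: measured connectivity = C + bE; behavioural change = E.

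Both give the same population correlation, r = b/√(1 + b²). For b = 0.5, r = 0.5/√1.25 = 0.45. The sham arm has no association in either case. The contrast is a Fisher-z difference with standard error √(2/13) = 0.39. Results from 20,000 simulated samples with 16 per arm:

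| b | Population r | Mean sample r (both) | Correlation p < 0.05: prediction / carry-over | Sham contrast p < 0.05: prediction / carry-over |
|---|---|---|---|---|
| 0.25 | 0.24 | 0.23 | 15% / 14% | 10% / 10% |
| 0.50 | 0.45 | 0.43 | 42% / 43% | 23% / 24% |
| 0.75 | 0.60 | 0.59 | 73% / 73% | 44% / 44% |
| 1.00 | 0.71 | 0.69 | 91% / 91% | 64% / 64% |

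With b = 0 the correlation test rejects in 5% of samples in both models. The sham contrast can show that an association belongs to active stimulation, but not which came first. The reward-evaluation contrast has the same limit: a connectivity change tied to goal-directed behaviour need not be related to reward-evaluation, and neither need a true predictor.

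**3. Illustrative size under weaker carry-over.** Suppose pre-stimulation connectivity predicts nothing, stimulation shifts connectivity with an SD of k times its between-person SD, and the shift correlates ρ with the behavioural change. Then r = ρk/√(1 + k²).

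- k = 0: r = 0, rejection rate 5%.
- k = 0.2, ρ = 0.5: r = 0.10/√1.04 = 0.10, rejection rate about 6%.
- k = 0.5, ρ = 0.7: r = 0.35/√1.25 = 0.31, rejection rate about 22%.

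The documents give neither k nor ρ. These values show only that the effect runs from nothing to material.

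**The case against.** The strongest reply is that carry-over is hypothetical. The after-effects described in sections 3 and 8.1.1 are recorded right after stimulation, and section 6.5 describes target engagement as acute. Nothing in the documents shows that one session alters fMRI connectivity until a separate visit. This stands, and it limits the point to what can be concluded. It does not rescue the predictive wording, because nothing planned excludes the alternative and the interval that would help to judge it is not recorded.

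It is also fair that the planned test is a correlation, that the outcome column of section 3 says so, that the protocol proposes no selection of patients by connectivity, and that this is one exploratory outcome of a pilot with an optional scan. The objective, the hypothesis and section 9.4.4 still state prediction.

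A reader might also infer from section 7.1 ("Discontinuation of stimulation during session 1 means that study participation is halted and no other sessions are completed") that connectivity is missing according to what happened during treatment. The documents do not support this for the analysed set. Section 9.3 already limits analysis to people who complete the intervention, so those who stop are outside the correlation whenever the scan takes place. Sections 7.2 and 9.3 differ on whether such people are replaced, but that does not change who is analysed.

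Simply exchanging Sessions 2 and 3 is not free either. Section 4.1 fills the rest of the scan slot with as many EEfRT blocks as fit. A swap would therefore give a variable amount of practice on the primary-outcome task before titration and the baseline blocks.

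**Conclusion.** The point holds as a limit on inference. As designed, exploratory outcome 2 can show an association between the behavioural response and connectivity measured after stimulation. It cannot show that connectivity predicts the response, and neither planned comparison closes the gap. This rests on the order of sessions alone and needs no assumption about effect size.

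A reader might go further and infer that the correlation is biased, or that stimulation is known to alter connectivity at Session 3. The documents support neither. With no carry-over there is no bias, and the rejection rates of about 6% to 22% depend on assumed inputs. Primary and secondary outcomes do not use the MRI and are unaffected. The point is modest in weight, but it is worth acting on because correcting the claim costs almost nothing.

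**What to change.** **Main change.** In sections 3, 9.1 and 9.4.4, replace *predicts* and *predictive of* with *associated with connectivity measured after stimulation*. Record and report the stimulation-to-scan interval for each participant. State that the result does not establish pre-treatment prediction. The cost is wording and one recorded variable.

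**Optional partial check.** Compare mean Session 3 connectivity across the three randomised arms. With 16 per arm, a pairwise comparison needs a standardised difference of about 1.0 for 80% power and has about 28% power at 0.5. A null result would therefore not exclude carry-over, and equal means would not exclude shifts that differ between individuals according to response.

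**If the predictive claim is to be kept.** Acquire the structural and resting-state scans after Session 1 eligibility and before stimulation. Leave the EEfRT out of that scan so that the primary-outcome task is not practised beforehand, and have written consent and the pregnancy check in place for that visit. The costs are the loss or separate scheduling of task fMRI, some scans spent on people who do not go on to stimulation, and an extra visit before the session that the primary outcome needs. That is a real trade-off for an exploratory outcome and is for the sponsor to weigh.

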9.4.6 BASELINE DESCRIPTIVE STATISTICS

All baseline descriptive statistics will be analyzed either using paired t-tests with random effect "participant" or chi-square tests where deemed appropriate. Descriptive statistics will be described based on the **General Approach described in 9.4.1**.

9.4.7 PLANNED INTERIM ANALYSES

If there is an unexpected event that is related to tACS, then a blinded interim descriptive analyses on the safety measures (blinded adverse effects and responses to the stimulation questionnaire) will be performed. If there is a reason to review unblinded information, a researcher not involved in the data collection for the study, [name] or another researcher in the group, will be access the list of

participant identification numbers kept by [name]. Participant identification numbers will be in a table according to the two arms of the study; however, the treatment of each arm will not be disclosed. This information will allow the researcher to compare the two groups.

There are no other planned interim analyses.

9.4.8 SUB-GROUP ANALYSES

Sub-group analyses will not be used in this study, as the sample size is too small to conduct analyses based on age, sex, race/ethnicity, or other demographic characteristic(s).

10 SUPPORTING DOCUMENTATION AND OPERATIONAL CONSIDERATIONS

10.1 REGULATORY, ETHICAL, AND STUDY OVERSIGHT CONSIDERATIONS

10.1.1 INFORMED CONSENT PROCESS

10.1.1.1 CONSENT/ASSENT AND OTHER INFORMATIONAL DOCUMENTS PROVIDED TO PARTICIPANTS

Informed consent is a process that is initiated prior to the start of the study and continues throughout the individual's study period. The potential benefits of tACS will be provided to the participants and their families. Consent forms describing, in detail, the study intervention, device, procedures, and risks are given to the participant and written documentation of informed consent is required prior to the administration of any treatment. Electronic consent will be documented via REDCap before the initial interview assessments. All consent forms will be IRB-approved and updated with any new information as modifications are made throughout the study.

10.1.1.2 CONSENT PROCEDURES AND DOCUMENTATION

During a phone call, the researcher and potential participants will review the clinical trial in its entirety. At several intervals during the consent review, the researcher will ask questions that will assess the comprehension of the information in the consent. If the participant is unsure or does not know, the researcher will return to that section and more carefully explain the information. Participants must complete the eConsent documentation via REDCap prior to any additional procedures taking place. If needed, the participants will have the opportunity to discuss the study with their surrogates or think about it prior to agreeing to participate. Participants will be informed that participation is voluntary and that they may withdraw from the study at any time, without prejudice.

At the beginning of the first visit to the lab, participants will sign a physical copy of the consent document witnessed by research personnel. A copy of the signed informed consent document will then be given to the participant for their records. The rights and welfare of the participant will be protected by emphasizing to them that the quality of their medical care will not be adversely affected if they decline to participate in this study.

10.1.2 STUDY DISCONTINUATION AND CLOSURE

This study may be temporarily suspended or prematurely terminated if there is sufficient reasonable cause. If the study is prematurely terminated or suspended, the Principal Investigator (PI) will promptly inform research staff, study participants, and the IRB and will provide the reason(s) for the termination or suspension. Study participants will be contacted, as applicable, and be informed of changes to study visit schedule.

Circumstances that may warrant termination or suspension include, but are not limited to:

- Determination of unexpected, significant, or unacceptable risk to participants
- Insufficient compliance to protocol requirements
- Data that are not sufficiently complete and/or evaluable

Study may resume once concerns about safety, protocol compliance, and data quality are addressed, and satisfy the IRB.

10.1.3 CONFIDENTIALITY AND PRIVACY

Participant confidentiality and privacy is strictly held in trust by the participating investigators, their staff, and the research team. This confidentiality is extended to cover testing of biological samples and genetic tests in addition to the clinical information relating to participants. Therefore, the study protocol, documentation, data, and all other information generated will be held in strict confidence.

All research activities will be conducted in as private a setting as possible.

All data will only be referenced by dummy identifier code. Data will be stored on a password protected computer. A key connecting names and identifier code numbers will be kept in a locked cabinet, accessible only by research personnel. All data will be stored and analyzed on password protected computers, also only accessible by research personnel. Participants will not be identified in any report or publication about this study and there is no risk of deductive disclosure. At the end of the study, all records will continue to be kept in a secure location for as long a period as dictated by the IRB.

Study participant research data, which is for purposes of statistical analysis and scientific reporting, will be entered into TraCS Clinical Research Data Management Service (REDCap). The database system provides secure web-based data entry with the data stored on servers that are maintained by TrACS. The data is encrypted during transmission. The servers are located in a secure campus area with all appropriate physical security measures in place. The web and database servers are monitored by the TraCS IT staff, patched frequently, and scanned by a third-party vendor to ensure that they are protected against known vulnerabilities. The scanning application is the standard service for the entire campus. Access is by individual user id and is restricted to the forms and/or functions that the user needs to have.

